18 SECONDARY OUTCOME MEASURES

Analysis of secondary outcome measures will use the same approach as the primary outcome measure if the outcome is binary. Wilcoxon rank-sum tests will be used to compare the continuous secondary outcome measures between groups. Jonckheere-Terpstra tests will be used to assess trends across the groups. Rank-based Spearman correlations will describe association between outcome measures. Scatter plots may also be used to present associations between outcome measures. Plots showing median, Q1 and Q3 values over time will also be presented, overall and by study group.

18.1 HIV-1-specific CD4+ and CD8+ T-cell responses to nef, gag, pol and env by flow cytometry while HIV-1 RNA is suppressed on ART

The following HIV-1-specific responses will be summarized:

- a. Percent of CD4(8) cells expressing each of the 5 cytokines (CD40L, CD107a, IFN γ , MIP1B, TNF α) in responses to each of the 4 protein stimulants (ENV, GAG, NEF and POL)

Parent: CD3+CD4+ or CD3+CD8+

Cytokine Markers: CD40L+; CD107a+; IFN γ +; MIP1B+; TNF α + each individually

- b. Percent of CD4(8) cells expressing any cytokine (total response) to each of the 4 protein stimulants

Parent: CD3+CD4+ or CD3+CD8+

Cytokine Marker: CD40L+ or CD107a+ or IFN γ + or MIP1B+ or TNF α +

- c. Relative proportion of CD4(8) cells co-expressing any 2/3/4/5 cytokines (polyfunctional responses) to each of the 4 protein stimulants

Parent: CD3+CD4+Cytokine+ or CD3+CD8+Cytokine+

For each n-cytokine polyfunctional response, the response is calculated as the total of the relative percent of cells expressing exactly n cytokines for the various combinations. For example, for 4-cytokine polyfunctional response, the various combination of the 4 positive cytokines are:

CD40L-;CD107a+;IFNg+;MIP1B+;TNFa+

CD40L+;CD107a-;IFNg+;MIP1B+;TNFa+

CD40L+;CD107a+;IFNg-;MIP1B+;TNFa+

CD40L+;CD107a+;IFNg+;MIP1B-;TNFa+

CD40L+;CD107a+;IFNg+;MIP1B+;TNFa-

And similarly, for 3-cytokine polyfunctional response, there are 10 various combinations with 3 positive cytokines.

Note:

For response a) and b) above, the results for a specific outcome for a specific participant/specimen-date are calculated by subtracting the corresponding background control value (media control). If the result would be less than zero after background subtraction, the result is set to zero. If the result of the active control SEB is less than the result of the background control for a particular outcome, the observation for that participant/specimen-date is treated as no result generated and is not included in the statistical analyses or plots.

For response c), since the percentage is among cells which expressing at least one cytokine, there is no need to subtract the corresponding background control value. However, if the result of the active control SEB is less than the result of the background control for any cytokine response (response a above), then the observations with the parent CD3+CD4(8)+cytokine+ are treated as no result generated and is not include in the calculation of response c.

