2.6 Hypotheses

Timing of antiretroviral therapy (ART) during different stages of acute HIV-1 infection (AHI) will be predictive of the magnitude and characteristics of HIV-1 reservoirs, and the quantity and quality of HIV-1-specific immune responses at week 48 on Step 1.

- ART initiation prior to HIV-1 antibody detection will be associated with limited or no detectable proviral DNA or HIV-1-specific immune responses at week 48 on Step 1.
- ART initiation in later AHI stages will be associated with larger HIV-1 reservoir establishment and quantitatively and qualitatively different HIV-1-specific immune responses at week 48 on Step 1.

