18.2 Cell-associated HIV-1 DNA in participants prior to ART initiation

Pre-ART cell-associated HIV-1 DNA will be summarized using the same approach as week 48 CAHD.

Fold-changes (absolute change in the log₁₀-transformed measurements) from pre-ART measurement in CAHD will be summarized using a similar approach.

Correlations between selected immunology responses (IFNg+ and total response) and week 48 CAHD will be examined using Spearman correlation coefficient (primary analysis population) with and without controlling for the study group.

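### SAP 18.1 zeroes negative background-subtracted T-cell responses before the rank tests; where net responses are near zero, a difference in background noise between Fiebig groups would then appear as a difference in rank

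*SAP*

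**What the plan says.** SAP 18.1 lists three kinds of HIV-1-specific response. Response (a) is the percentage of CD4+ or CD8+ cells expressing each cytokine, and (b) is the percentage expressing any cytokine. For both, the media-control value for the same participant and specimen date is subtracted, and then: "If the result would be less than zero after background subtraction, the result is set to zero".

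The only screen on control quality drops an observation under this condition: "If the result of the active control SEB is less than the result of the background control for a particular outcome". Response (c), the polyfunctional proportion, is neither subtracted nor zeroed, because "there is no need to subtract the corresponding background control value".

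SAP 18 sets the tests: "Wilcoxon rank-sum tests will be used to compare the continuous secondary outcome measures between groups", and "Jonckheere-Terpstra tests will be used to assess trends across the groups". SAP 18.2 adds: "Correlations between selected immunology responses (IFNg+ and total response) and week 48 CAHD will be examined using Spearman correlation coefficient", with and without control for study group.

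The SAP gives no positivity threshold for these responses, no background values, no comparison of background between groups and no analysis on unzeroed values. Protocol 10.3 states that there is no randomization. Protocol 10.4 calls the secondary objectives largely exploratory.

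**The concern.** When a specimen has no true HIV-specific response, stimulated minus media scatters around zero. The rule collapses the negative half of that scatter into ties and leaves the positive half as it is. A rank test on signed differences is centred correctly even when two groups have different noise. After zeroing it is not, because the noisier group keeps its larger positives and loses its equally large negatives.

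The rule acts only on values below zero, so it matters most where responses are weak. SAP 2.6 expects this for the earliest-treated group: "limited or no detectable proviral DNA or HIV-1-specific immune responses at week 48 on Step 1". Protocol 10.4 expects gag CD4+ responses in only 15% of Fiebig I/II and 30% of Fiebig III/IV, so most participants in two of the three groups may lie near zero.

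The rule covers 5 cytokines × 4 stimulants × 2 subsets = 40 outcomes of type (a) and 4 × 2 = 8 of type (b), 48 in all. At stake is whether a stage difference in these outcomes reflects HIV-specific response or assay background.

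**Working it through.** **Inputs from the documents.** n = 42 per group and type I error 0.05 per pairwise comparison (Protocol 10.4, stated for the primary endpoint and carried over here as an assumption, taken as two-sided). Expected gag CD4+ response rates of 15%, 30% and 80% (Protocol 10.4).

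**Assumptions.** Net response is normal, in units of the quieter group's noise SD. The noise SD ratio r between groups is varied because the documents give no background values.

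**1. The plan's own figure.** The documents state no figure for the zeroed rank analysis. The nearest is the power quoted for gag responses. Exact two-sided Fisher power with 42 per group is 30.05% for 15% v 30% (stated 30%), 99.7% for 30% v 80% and above 99.9% for 15% v 80% (both stated >90%). These reproduce.

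**2. Size of the rank shift under no true response.** Let X have SD 1 and Y have SD r, both centred at zero. After zeroing, each sign combination has probability 1/4:
- both negative: a tie, counted 1/2
- Y positive, X negative: counted 1
- Y negative, X positive: counted 0
- both positive: Y exceeds X with probability (2/π)·arctan(r)

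So P(Y ranks above X) = 1/8 + 1/4 + (1/4)(2/π)·arctan(r) = 0.375 + arctan(r)/(2π). This gives 0.500 at r = 1, 0.531 at 1.5, 0.551 at 2 and 0.574 at 3. With signed values it is 0.500 at every r.

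**3. Wilcoxon rejection under no true response** (20,000 simulated trials per row, tie-corrected, nominal 5%):

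| Noise SD ratio | Signed | Zeroed |
|---|---|---|
| 1 | 4.6% | 4.8% |
| 1.25 | 5.1% | 6.1% |
| 1.5 | 5.3% | 8.0% |
| 2 | 5.7% | 14.0% |
| 3 | 6.9% | 24.2% |

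At r = 2, 13.7 of the 14.0 points favour the noisier group.

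**4. Trend test.** With the middle group's SD at the geometric mean of the outer two, Jonckheere-Terpstra rejection (signed v zeroed) is 4.9% v 8.6%, 5.5% v 14.6% and 6.8% v 27.1% at outer-group ratios of 1.5, 2 and 3. Spearman was not simulated.

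**5. What the ratios mean in background terms.** For Poisson event counts (assumed 100,000 cells per tube, reference background 0.02%), noise SD grows as the square root of background. A ratio of 2 therefore needs a 4-fold background difference and a ratio of 3 a 9-fold one. Zeroed v signed rejection is 5.8% v 4.8% at 1.5-fold, 8.1% v 5.2% at 2-fold and 15.6% v 5.5% at 4-fold.

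**6. Effect of a real response.** At r = 2 with a common response of 0.5, 1 and 2 SD, zeroed rejection is 7.6%, 5.9% and 5.9%, against 5.7%, 5.6% and 5.9% signed.

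**7. Power** (signed v zeroed):
- Equal noise, one group at 0 and the other at 0.25, 0.5, 0.75 or 1.0 SD: 19.9% v 17.9%, 59.9% v 55.1%, 91.2% v 88.7%, 99.3% v 99.0%.
- Equal noise, responder shares 15% v 30%: 21.1% v 22.2% for a 3 SD response and 9.4% v 9.7% for 1 SD. Zeroing gains slightly.
- Equal noise, 15% v 80%, 1 SD response: 78.0% v 75.9%.
- r = 2 with the noisier group null and the other at 0.5, 0.75 or 1.0 SD: 29.7% v 13.7%, 55.0% v 36.7%, 78.6% v 67.2%.

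**8. Summaries.** In a null group the median is 0 and Q3 is the same with or without zeroing. Q1 rises to 0, and the mean rises by about 0.4 × the noise SD (1/√(2π) = 0.399).

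**The case against.** The strongest answer is that the false signal needs two conditions together, and the documents make only one of them plausible. Near-zero responses are hypothesised, but nothing says that media background differs by Fiebig group. Every group has the same specimen-level subtraction and the same SEB screen, and all are assessed while suppressed on ART. With equal noise, zeroing does no harm to the error rate. A ratio of 2 needs roughly a 4-fold background difference across a whole group, and a 2-fold difference gives only about 8%. All of this stands, and it makes the point conditional. It does not remove it: the groups are not randomised, so equal background is not assured by design, and the SAP plans no check of it.

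Zeroing also has a use. A percentage of responding cells cannot be negative, and one variable then serves tests, plots and summaries. That is fair, but rank methods do not need non-negative data.

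Three stronger readings are tempting and are not supported:
- A reader might infer that the noisier group would be classed as responders. SAP 18.1 defines no responder, and null-group medians and Q3 do not move.
- A reader might infer a general loss of power. At equal noise the loss is 0 to 5 points for pure shifts with one group at zero, and there is none in the 15% v 30% patterns. A large loss (about 11 to 18 points) appears only if the null group is also the noisier one.
- A reader might infer a bias towards the Group 1 hypothesis. The direction depends on which group is noisier, and the documents do not say.

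**Conclusion.** The point holds conditionally. Zeroing before the rank-based analyses converts a difference in background noise into a difference in rank when net responses are near zero. At assumed noise SD ratios of 1.5, 2 and 3, with 42 per group, normal noise and no true response, Wilcoxon rejection is about 8%, 14% and 24%, against about 5%, 6% and 7% on signed values. At equal noise, or once a common true response reaches about 1 SD, the inflation is absent or negligible. Whether the trial is affected cannot be told from the documents, because they report no background values. This is a cheap improvement to a secondary, largely exploratory outcome. Response (c) and the primary CAHD comparison are not affected.

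**What to change.** In SAP 18.1, state that the Wilcoxon, Jonckheere-Terpstra and Spearman analyses of responses (a) and (b), including the correlations in 18.2, use the signed background-subtracted value. At minimum, pre-specify that version as a sensitivity analysis beside the zeroed one. Keep zeroed values for plots and displayed summaries. Report media-control background and the share of zeros by Fiebig group, so that readers can judge whether noise was comparable. Leave the SEB rule unchanged.

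The cost is one sentence, one derived variable and a short table, with no new data. The downsides are negative percentages in the analysis dataset, tested values that differ from displayed values, and a possible loss of 1 to 3 points of power in some responder-mixture patterns (for 15% v 30% at 3 SD, 22.2% − 21.1% = 1.1 points). If noise proves equal across groups, the signed test stays near nominal (4.6%), so the change is safe even if the concern does not materialise.

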6.4.8 Immunologic Studies

CD4+/CD8+ T-cells

Obtain absolute CD4+/CD8+ T-cell count and percentages during the study from a laboratory that possesses a **CLIA certification or equivalent (US sites) or IQA certification (non-US sites)**.

In Step 2, record the results from the laboratory tests (if available) that are performed as part of routine care. Do not perform if results are not available from routine care.

HIV-1-Specific T-Cell Responses

PBMC and plasma will be collected, frozen, and stored for studies of HIV-1-specific T-cell responses. In addition, the PBMC samples will be shipped in batch for HLA typing and CCR5 delta-32 genotyping at the end of the study. Please refer to the A5354 LPC for instructions related to the collection, processing, and shipping of these samples.

Participants will have **blood collected for PBMC and plasma storage at the visits indicated in the SOE. At the Step 1 entry visit, PBMC and plasma will be obtained from large volume blood collection (or the optional leukapheresis, as an alternative to the large volume blood draw).**

At week 49 (if needed), blood collected may be pooled with, or tested in lieu of, blood collected at Step 1 week 48 to obtain a sufficient quantity for any assays.

At weeks 60 and 72 **on Step 1, PBMC and plasma storage will be obtained.**

For participants who started ART during Fiebig VI, PBMC and plasma storage will not be performed at weeks 12 and 24 **after Step 1 entry.**

For participants who interrupt ART for ≥ 7 consecutive days before **Step 1** week 48 of the study, their last PBMC and plasma storage will be at week 48 **on Step 1**. If such interruption occurs after week 48, no PBMC and plasma storage will be performed at future visits.

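### SAP 18.1 sets no minimum SEB response, so a specimen whose cells cannot respond passes the check on each single-marker or total outcome at least half the time

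*SAP*

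**What the plan says.** SAP 18.1 defines three kinds of response, separately for CD4 and CD8 cells. Response (a) is "Percent of CD4(8) cells expressing each of the 5 cytokines" for each stimulant, (b) is the percent expressing any of the five (the total response), and (c) is the polyfunctional breakdown among cytokine-positive cells.

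For (a) and (b) the media value is subtracted and the result is floored: "If the result would be less than zero after background subtraction, the result is set to zero". The positive-control rule reads: "If the result of the active control SEB is less than the result of the background control for a particular outcome". When that happens the observation "is treated as no result generated and is not included in the statistical analyses or plots". The rule states no minimum SEB response or margin.

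For (c) there is no background subtraction, and the whole cytokine-positive parent is voided under a different condition: "if the result of the active control SEB is less than the result of the background control for any cytokine response".

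On testing, SAP 18 says: "Wilcoxon rank-sum tests will be used to compare the continuous secondary outcome measures between groups". SAP 18.2 adds Spearman correlations of the IFNg and total responses with week 48 cell-associated HIV-1 DNA (CAHD).

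Protocol 6.4.8 describes the material: "PBMC and plasma will be collected, frozen, and stored for studies of HIV-1-specific T-cell responses". It refers to a Laboratory Processing Chart, which is not among the documents supplied. Neither document gives a viability, cell-count or minimum-SEB criterion for this assay.

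**The concern.** A positive control should show that the cells in the well are able to respond. Requiring only that SEB is not below media does not show that. When the cells cannot respond, SEB and media are two readings of the same background, and which one is higher is a matter of chance.

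A failed specimen that passes contributes an antigen-minus-media difference made only of noise, cut off at zero. In the data set it looks like a participant whose live cells did not recognise the antigen. SAP 2.6 predicts that ART begun before antibody detection goes with "limited or no detectable proviral DNA or HIV-1-specific immune responses at week 48 on Step 1", so low values carry meaning in this study. Extra failures in one Fiebig group would shift that group's comparison. The SAP does not ask for voided results to be counted by group, so an imbalance would not be seen.

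**Working it through.** **1. The plan's own figure.** The only quantitative statement on this outcome is in Protocol 10.4: gag-specific CD4 responses of 15% (Fiebig I/II), 30% (III/IV) and 80% (V), with 30% power for I/II versus III/IV and over 90% for V versus each of the others. With 42 per group, a two-sided Fisher's exact test and alpha 0.05 (the settings stated for the primary endpoint), exact enumeration gives 0.3005 for 15% v 30%, 0.997 for 30% v 80% and above 0.999 for 15% v 80%. The stated figures are reproduced.

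**2. Chance that a failed specimen passes one (a) or (b) outcome.** Assumption, not in the documents: SEB, media and antigen wells are exchangeable when the cells cannot respond. By symmetry P(SEB > media) = P(SEB < media), and a tie passes, so

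P(pass) = 0.5 + P(tie)/2.

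The tie rate depends on the scale of the data, which the documents do not give:

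- No ties: 0.50.
- Ties only when both wells read zero (percentages with differing denominators), Poisson mean m per well: 0.5 + exp(-2m)/2. At m = 1 this is 0.5 + 0.135/2 = 0.57; at m = 5 or more it is 0.50.
- Ties at any equal integer count: 0.52 (m = 50), 0.56 (m = 5), 0.65 (m = 1), 0.91 (m = 0.1).

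The lower bound of one half holds in every case.

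**3. What is recorded after a pass.** Without ties, the six orderings of the three wells are equally likely. A floored zero given a pass requires antigen < media < SEB, so its probability is (1/6)/(1/2) = 33%. The other 67% are small positive noise. With integer counts at m = 0.1, 91% are exactly zero.

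**4. Effect of balanced failure on the gag comparison.** Let d be the assumed share of failed specimens and let half of them pass. Their share of kept results is f = 0.5d/(1 - d + 0.5d), and each response rate is multiplied by (1 - f). With 42 kept results per group:

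| d (assumed) | f | Rates I/II, III/IV | Power |
|---|---|---|---|
| 0 | 0 | 15.0%, 30.0% | 30% |
| 5% | 0.025/0.975 = 2.6% | 14.6%, 29.2% | 29% |
| 10% | 0.05/0.95 = 5.3% | 14.2%, 28.4% | 28% |
| 20% | 0.10/0.90 = 11.1% | 13.3%, 26.7% | 26% |
| 30% | 0.15/0.85 = 17.6% | 12.4%, 24.7% | 23% |

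At 5%, 0.05 × 42 = 2.1 specimens per group fail and about one is kept.

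**5. Effect of unbalanced failure.** If two groups shared a true 30% rate and only one had d = 20%, its observed rate would be 0.30 × (1 - 0.111) = 26.7%, a false difference of 3.3 points. At a shared 80% rate the false difference would be 0.80 × 0.111 = 8.9 points. These are illustrations; the documents give no failure rate for any group.

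**6. What a margin would do.** As an example, require SEB - media > 1.96 × sqrt(SEB + media) in event counts (one-sided 2.5%). The pass rate of a failed specimen falls from 0.65 to 0.007 at m = 1, from 0.56 to 0.022 at m = 5, and from 0.52 to 0.025 at m = 50.

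**The case against.** The strongest reply is that the effect is small and conditional. These are secondary outcomes that Protocol 10.4 calls largely exploratory, no failure rate is documented, and the laboratory may reject dead specimens under criteria outside the SAP. That stands, and it limits the size of the point. It does not supply the missing criterion in the SAP's own rule.

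Four stronger readings are tempting, and the documents do not support them.

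- **A failed specimen passes well over half the time, and almost always on some marker.** The excess over 50% comes entirely from ties. With independent markers and no ties, at least one of five passes 97% of the time and (c) is voided 97% of the time. The five markers are read in the same cells, however, and at correlation 0.8 both figures fall to about 71%. Response (b) is compared once, on the any-cytokine total, so the five-marker figure does not apply to it or to the single IFNg outcome in SAP 18.2.
- **The two SEB rules are inconsistent.** The text gives a reason for the difference: (c) uses a pooled cytokine-positive parent without background subtraction, so one bad marker affects its denominator.
- **Assay failure is scored as true absence and so supports the hypothesis.** SAP 18.1 defines no responder category, and without ties only a third of passing values are exactly zero. Balanced failure shrinks group differences, which works against the hypothesis of differing responses by stage. Imbalance is possible, since Groups 2 and 3 closed to enrolment while Group 1 continued and storage time could differ, but nothing in the documents shows it.
- **One any-marker check should replace the present ones.** That would loosen (c), and would admit to (a) a marker whose own control failed.

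The wording for (a) and (b) could also be read as voiding the whole specimen-date. The missing margin remains on that reading.

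**Conclusion.** The point holds for responses (a) and (b). The rule has no minimum SEB response, so under exchangeable wells a non-responsive specimen passes each outcome at least half the time and enters the Wilcoxon tests and the CAHD correlations as zero or near-zero noise.

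Its size is conditional on a failure rate that the documents do not give. With balanced failure the loss is slight at 5% (gag power about 30% to 29%) and reaches 23% power only if 30% of specimens fail. Those power figures use the protocol's responder percentages and assume that half of the failed specimens pass with 42 results kept. The more serious case is failure that differs by Fiebig group: it would bias the secondary comparisons, and the plan neither guards against it nor reports it. The primary outcome does not use this assay.

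**What to change.** Keep the outcome-level SEB check for (a) and (b) and the any-cytokine check for (c). Add to SAP 18.1 a specimen-level criterion for each T-cell subset (CD4, CD8): the total (any-marker) SEB response must exceed media by a pre-specified minimum, set by the assay laboratory blind to Fiebig group, for example by a one-sided count test. If a specimen fails, treat (a), (b) and (c) as missing for that specimen and subset. Report the number voided by study group. If the laboratory already applies such a threshold, cite it in SAP 18.1 and report the counts.

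The cost is a paragraph of SAP text, one data filter and a few more missing results. Some may be live specimens with a weak SEB response; the documents give no SEB values from which to estimate how many.

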Based on the available Fiebig staging data as of May 15, 2019, after the completion of centralized testing, 31% of participants estimated to be in Group 1 were determined to be in Group 1, while 50% were determined to be in Group 2. Group 1 has enrolled 37 participants. Group 2 had enrolled 63 participants, and Group 3 had enrolled 54 participants. Assessing the current group counts and rates, we anticipate that, with 196 participants enrolled (an additional 36 enrollments after replacing Fiebig VI and HIV negative participants), approximately 50 participants will be determined to be in Group 1.

Secondary objectives are largely exploratory without formal sample size calculation. However, based on data from the RV254 study, HIV-1-specific CD4+ T-cell responses to gag after ART are expected to be 15% in Fiebig I/II versus 30% in Fiebig III/IV versus 80% in Fiebig V which will provide 30% power for Fiebig I/II versus III/IV, >90% power for Fiebig V versus the other two groups.

It is anticipated that the study will take **36 months to accrue** with one third of the participants accrued during the first 6 months after at least three international sites have enrolled at least one participant.

10.5 **Data and Safety** Monitoring

Accrual, baseline characteristics (including baseline laboratory values), conduct of the study (including premature study discontinuations, data availability and sample acquisition), any ART interruptions, VFs, and all reported toxicities and AEs will be monitored by the team during the study. The team will also closely monitor the Fiebig stages of the study population as defined by the standardized testing of samples obtained at ART initiation. In addition, the study will be reviewed by a Study Monitoring Committee (SMC) according to ACTG standard operating procedures. The SMC will review accrual, baseline characteristics (including baseline laboratory values), Fiebig stage at ART initiation, AE summaries, CD4+ T-cell counts and HIV-1 RNA levels/suppression over time, study and ART discontinuations (and reasons), and completeness of follow-up and sample availability. The SMC will convene, at a minimum, 6 months after the first participant is enrolled or after 25 participants are enrolled, whichever is earlier and approximately annually thereafter or at the request of the SMC.

Furthermore, the CMC or the team may, at any time it thinks appropriate, ask for the SMC to independently review all available safety data.

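### SAP 18.1 exempts the polyfunctional T-cell proportions from background correction for a reason that does not hold, so group comparisons of response quality can be confounded with response magnitude

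*SAP*

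**What the plan says.** SAP section 18.1 defines three families of outcome for CD4+ and CD8+ cells, using four protein stimulants and five markers: (a) each marker singly; (b) "Percent of CD4(8) cells expressing any cytokine (total response) to each of the 4 protein stimulants"; and (c) the relative proportion co-expressing two, three, four or five markers. The denominator of (c) is given as "Parent: CD3+CD4+Cytokine+ or CD3+CD8+Cytokine" (that is, cytokine-positive cells), and for each n "the response is calculated as the total of the relative percent of cells expressing exactly n cytokines for the various combinations".

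The Note to 18.1 says that (a) and (b) are "calculated by subtracting the corresponding background control value (media control"), and that "If the result would be less than zero after background subtraction, the result is set to zero". For (c) it says that "since the percentage is among cells which expressing at least one cytokine, there is no need to subtract the corresponding background control value". The only filter on (c) drops observations where the SEB active control falls below the media control for any single-cytokine response.

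Under section 18, continuous secondary measures are compared between groups by Wilcoxon tests, and "Jonckheere-Terpstra tests will be used to assess trends across the groups". Response (c) is how the SAP addresses the quality part of its first secondary objective (SAP 2.7.2, item 1b).

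**The concern.** Restricting attention to cytokine-positive cells does not remove cells that are positive without antigen. The SAP accepts that such cells exist, because it subtracts them from (b), and (b) counts exactly the cells that form the denominator of (c). In (c) they remain above and below the line.

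Two consequences follow. First, a weak response gives a share close to the background's own co-expression profile, and a strong response gives one close to the antigen-specific profile. Second, a sample whose (b) is set to zero still receives a value for (c), and that value is essentially background. Nothing limits (c) to responders. The SEB rule checks assay validity, not whether the HIV response exceeds background.

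This matters because the design expects magnitude to differ by group. Protocol 10.4 states that "HIV-1-specific CD4+ T-cell responses to gag after ART are expected to be 15% in Fiebig I/II versus 30% in Fiebig III/IV versus 80" (the last figure is the percentage for Group 3), and the first sub-hypothesis (SAP 2.6) foresees little or no response in Group 1. The second sub-hypothesis predicts only that quality will differ, without a direction, so an artefact either way could be read as support.

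**Working it through.** **The plan's own figure.** The 15/30/80% for CD4+ gag carry a stated power of 30% for Group 1 v Group 2 and above 90% for Group 3 v either. Exact two-sided Fisher power at n = 42 per group is 30.0% for 15% v 30%, 100% for 15% v 80% and 99.7% for 30% v 80%. The stated figures reproduce when 15/30/80% are read as responder proportions.

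**Mixture.** Let S be the antigen-specific frequency, B the background frequency, and qs and qb their polyfunctional shares. Under the SAP rule,

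observed share = (S·qs + B·qb) / (S + B).

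The documents give none of these values. Assume B = 0.05% and qs = 0.40 for everyone:

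| qb | S = 0 | S = 0.05% | S = 0.2% |
|---|---|---|---|
| 0.05 | 0.05 | 0.225 | 0.33 |
| 0.30 | 0.30 | 0.35 | 0.38 |
| 0.40 | 0.40 | 0.40 | 0.40 |
| 0.50 | 0.50 | 0.45 | 0.42 |

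For example, qb = 0.05 and S = 0.2% give (0.2 × 0.40 + 0.05 × 0.05)/0.25 = 0.33. There is no bias at qb = qs, and its direction reverses when qb exceeds qs.

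**Simulation, CD4+ gag only.**
- From the documents: responder rates 15/30/80%.
- Assumed: 42 per group with flow data (Protocol 10.4 gives 42 for the CAHD comparison only); responders' S lognormal, median 0.2%, SD 0.4 log10; B lognormal, median 0.05%, SD 0.2 log10; 100,000 parent cells; Poisson counts in stimulated and media wells; qs beta with mean 0.40 and SD 0.12 in every group; 1,000 replicates; two-sided 0.05.

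Rejection rates of the Wilcoxon test under the SAP rule, when non-responders have no antigen-specific cells:

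| qb | 1 v 2 | 1 v 3 | 2 v 3 |
|---|---|---|---|
| 0.05 | 20% | 100% | 99% |
| 0.20 | 17% | 99% | 89% |
| 0.30 | 9% | 68% | 43% |
| 0.40 | 6% | 5% | 6% |
| 0.50 (direction reversed) | 8% | 66% | 43% |

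The same test at qb = 0.05, when non-responders have weak responses:

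| Non-responder median S | 1 v 2 | 1 v 3 | 2 v 3 |
|---|---|---|---|
| 0.02% | 13.0% | 96.5% | 82.4% |
| 0.05% | 8.0% | 65.3% | 44.3% |
| 0.10% | 5.7% | 18.0% | 12.2% |

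Further runs:
- At qb = 0.20, the 1 v 3 rate for the same three medians is about 75%, 35% and 10%.
- The trend test at qb = 0.05 rejects in 100% of trials with no non-responder response and 17.9% at a median of 0.10%.
- For the SAP's exactly-n outcomes (background and antigen-specific polyfunctional cells split alike over n, an assumption), the corresponding 1 v 3 rates are 99–100% and 10–18%.
- With responder rates of 60/70/80%, qb = 0.05 and no non-responder response, the rates are 13/34/12%. With equal responder rates they are about 5%.
- Samples with (b) = 0 that still receive a (c) value: 44/37/11% of Groups 1/2/3 with no non-responder response, 8/7/2% at a median of 0.02%, and about 2% or less at 0.05% and above.
- With media subtraction plus a responder gate, rejection is about 2–7% in every run at n = 42.

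**The case against.** The strongest reply concedes the logic and disputes the consequence.

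- **Impact is not shown by the documents.** They report neither background level nor background co-expression. If background and antigen-specific cells co-express alike, the SAP rule is nominal. This stands: the error of reasoning is certain, the size of its effect is not.
- **The largest rates come from an extreme case.** When non-responders have no antigen-specific cells, they have no true share, so rejection partly reflects a real difference in responder fraction. The labelling point stands, but it also illustrates the fault, because a difference in how many respond would be reported as a difference in quality. The weak-response runs avoid it: every participant then has a share drawn with mean 0.40, and 1 v 3 still rejects in 65.3% at a median of 0.05% (qb = 0.05).
- **The gradient is documented once.** The 15/30/80% cover CD4+ gag only. The other seven of the 2 × 4 = 8 lineage-by-antigen comparisons have no figure. This stands.
- **The remedy changes the estimand and costs sample size.** It describes responders only, a selection that differs by group. This stands and must be stated with the results, though a sample with no detectable response says little about response quality.
- **The corrected error rate assumes equal background in media and stimulated wells.** This stands as a limit of the check. The subtraction already planned for (a) and (b) rests on the same assumption.
- **Scope is narrow.** Protocol 10.4 describes the secondary objectives as largely exploratory. This stands.

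**Conclusion.** The concern holds. The exemption for (c) is wrong as written: its stated reason does not follow from the definitions in section 18.1, and it conflicts with the treatment of the same cells in (b).

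Bias needs two conditions: background and antigen-specific cells differ in co-expression, and magnitude differs by group. The protocol expects the second for CD4+ gag and is silent on the first. Under the assumptions above, error for Group 1 v Group 3 runs from nominal to 100%, and for Group 1 v Group 2 it never exceeds 24% in any run. These are illustrations of possible size, not estimates for this trial.

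The rule should be changed before the secondary immunology analysis is run. The primary CAHD analysis, responses (a) and (b), and the correlations in SAP 18.2 (which use IFNγ and total response) are not affected.

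**What to change.** Delete the exemption and replace it with these steps:

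1. For each Boolean cytokine combination, subtract the matching media-control frequency on the CD3+CD4+ or CD3+CD8+ parent.
2. Sum the net frequencies by number of markers (2, 3, 4, 5) and divide by the net total. Do not floor each combination at zero, since that keeps positive noise and discards negative noise across many sparse combinations. Flooring only the pooled totals made no material difference in the check.
3. Compute (c) only for samples that meet a pre-specified positive-response rule. The simulation used a total at least twice media and at least 20 net cells; the immunology laboratory should set the actual thresholds.
4. Report the number evaluable per group beside every (c) result, and state that (c) describes responders.

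If media values were not kept by combination, apply step 3 to the present (c) and call it a partial correction. At qb = 0.05, the gate alone gave about 4% error when non-responders had no response and responders' medians were equal. It gave 17% for 1 v 3 when the non-responder median was 0.02%, and 7/46/29% when that median was 0.05% and responders' medians were 0.1/0.2/0.4%.

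**Cost.** SAP wording and programming, with no new visits or samples. Whether media data were exported by combination must be checked; the documents do not say. Fewer samples are evaluable: about 6/12/30 of 42 if non-responders have no response, 24/26/35 if their median is 0.05%, and 33/34/37 at 0.10%. With true shares of 0.25/0.30/0.40, power for 1 v 2, 1 v 3 and 2 v 3 is about 10/60/58% in the first case and 29/99/83% in the second.
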